## **List of Abbreviations**

HIV	Human Immunodeficiency Virus
ASCVD	Atherosclerotic Cardiovascular Disease
CVD	Cardiovascular Disease
MI	Myocardial Infarction
HINTS	Hypertension Intervention Nurse Telemedicine Study
CITIES	Cardiovascular Intervention Improvement Telemedicine Study
CCM	Clinical Case Manager
PLWH	People Living With HIV
LDL	Low density lipoprotein
SBP	Systolic Blood Pressure

## Study Summary

Title	A Clinic-Based Case Manager Administered Telephone Intervention to Reduce Cardiovascular Disease Risk in Persons Living with HIV
Short Title	SWOBI-CVD
Protocol Number	Pro00085562
Phase	Phase 3
Methodology	Randomized Controlled Trial
Study Duration	24 months
Study Center(s)	Single-center
Objectives	To assess the impact of telephone-based case manager administered interventions in improving ASCVD risk factor outcomes among HIV-infected clinic patients.
Number of Subjects	50
Diagnosis and Main Inclusion Criteria	Patients diagnosed with HIV and either hyperlipidemia or hypertension
Duration of administration	24-weeks
Statistical Methodology	Generalized linear mixed regression models will be used to assess the changes in systolic blood pressure and LDL-c over the period of the intervention, accounting for repeated measurements within subjects as well as clustering of subjects within providers. Bivariable and multivariable analyses will be conducted for all covariates. To test for the effect of time on the differences in SBP and LDL-c between the groups, we will fit a constrained longitudinal data model (cLDA).  We will fit models with time as a categorical variable (based on the time of outcome measure collection) and as a continuous variable, to determine the best model fit.

## Introduction

### **1.1 Background and Significance**

*Scientific Premise:* Atherosclerotic cardiovascular disease (ASCVD) is now a leading cause of mortality in persons living with HIV (PLWH), accounting for approximately 10% of deaths in large HIV clinical cohorts. With widespread availability of effective antiretroviral therapy, deaths due to AIDS-related conditions will continue to decrease. Concurrently, ASCVD will continue to increase as a proportion of overall mortality among PLWH, especially in light of the aging HIV population. Multiple cohort studies have shown a 40-50% higher incidence of myocardial infarction (MI) among PLWH with suppressed viremia compared to uninfected persons. These observations highlight the need to adopt a comprehensive approach to decreasing ASCVD risk in this population, beyond durable viral suppression. Although chronic immune activation is thought to drive vascular inflammation and atherogenesis in PLWH, the higher prevalence of reversible ASCVD risk factors (smoking, hyperlipidemia and hypertension) among PLWH is also well established. Recent studies show that these risk factors are more deleterious in PLWH than in uninfected persons. As an example, in a large Danish cohort (n= 16,255), 72% of MIs observed among persons with HIV were at least partially attributable to smoking compared to 24% of MIs in uninfected persons. These data emphasize the need for investigating models of HIV care that are responsive to the complexities of ASCVD risk among PLWH.

Despite the increased risk of major ASCVD events in PLWH, ASCVD primary prevention in this group may be inferior to that of uninfected persons. A study at the University of Alabama showed that 17% of persons who were eligible for aspirin by USPSTF guidelines had received recommendations from their provider to take it. Similarly, data from our group showed that PLWH were 30% less likely to receive statins, 47% less likely to receive aspirin and 37% less likely to receive anti-hypertensives when indicated than age, sex and race matched controls. Unfortunately, behavioral interventions targeted at modifying provider practices pertaining to CVD risk reduction are often ineffective. Using non-physician clinical staff to augment care is a potentially effective way to overcome barriers to improving CVD risk management in this setting.

Behavioral interventions conducted by non-physician clinical staff are effective in reducing ASCVD risk. A meta-analysis of 39 randomized controlled trials assessing nurse and/or pharmacist-led CVD risk-reduction interventions, reported that systolic blood pressure dropped by 7.6mm Hg from baseline readings compared to usual care. The mean duration of the interventions assessed was only 8.3 months (range 3-13 months), demonstrating the rapid impact these interventions can have on CVD risk parameters. In a randomized study of 636 patients with hypertension, patients who received a 2-year nurse-administered behavioral intervention were 11% more likely to achieve blood pressure control than patients who received usual care. *The scientific premise of the proposed intervention is that clinical encounter supplementation provided by telephone, and delivered by trained professionals, will provide additional time and opportunity to establish and reinforce behaviors associated with CVD risk reduction. A measurable manifestation of this intervention will be reduction of blood pressure and low density lipoprotein (LDL) levels.*

***Significance of the Expected Research Contribution:*** With the large sample size of the retrospective analysis from Aim 1, findings from our study will provide insight into what care delivery models have worked historically for ASCVD primary prevention in PLWH. Our proposed study will also look at the utility of leveraging the unique, multidisciplinary structure of the HIV clinical care team for improving ASCVD outcomes in this high-risk population. If the proposed telephone-based intervention proves effective, similar interventions could be applied to addressing other non-AIDS chronic diseases including non-AIDS-related cancer, chronic kidney disease and osteopenia/osteoporosis. Our findings will also give validation to the paradigm of incorporating, non-provider HIV clinical staff into longitudinal chronic disease management initiatives for HIV clinic patients.

## **1.2 Innovation**

- 1) Our study will be the first comparative analysis to examine ASCVD-related outcomes based on models of healthcare delivery in an HIV population.** By 2019, 50% of all patients with HIV in the United States will be aged 50 or older. Understanding trends in chronic disease care delivery (particularly ASCVD primary prevention) in this aging population is critical to informing healthcare delivery interventions that are responsive to the ever-increasing burden of HIV clinical care. Although our data suggest that PLWH who receive medical care solely from HIV subspecialists are prescribed CVD medications less frequently than uninfected persons, how these outcomes deviate from PLWH receiving chronic disease care from non-HIV PCPs is unclear. The retrospective analysis proposed in Aim 1 will provide valuable insight on whether or not the intervention proposed in Aim 3 (and other interventions aimed at improving CVD risk management) should be restricted to persons who receive all non-AIDS chronic disease care exclusively from their HIV provider. In addition, no studies to date have looked at whether receiving CVD preventative care exclusively from an HIV provider has an adverse impact on hard CVD risk factor outcomes (successful blood pressure and lipid control). Our study will be the first to address this question.
- 2) The intervention design will be customized based on patient and provider input.** Telephone-based interventions have been previously shown to improve blood pressure in patients with hypertension. The framework of our proposed intervention will be based upon the nurse and pharmacist administered instruments from the Hypertension Intervention Nurse Telemedicine Study (HINTS) and the Cardiovascular Intervention Improvement Telemedicine Study (CITIES) respectively. However, implementing such interventions in the context of HIV care presents unique complexities. To better understand the nuances of HIV care relevant to the development of the intervention, we will adopt a mixed methods approach. Semi-structured interviews and focus groups of HIV clinic patients and clinical case managers will be used to inform our research team of precise ways to modify our proposed intervention to best fit the needs of the HIV clinic population. This approach will provide the unique opportunity to tailor a previously validated ASCVD risk management intervention to specifically meet the needs of HIV-infected persons.
- 3) The intervention will be generalizable, sustainable and time-efficient.** Unlike the HINTS and CITIES studies which were administered by nurses and pharmacists hired specifically for the research study, we will pilot our proposed intervention with clinical case managers (CCMs) who are primarily employed by the HIV clinic, and are part of many HIV clinics.

Given the prominent role of CCMs in HIV care, our intervention (if effective) will be highly generalizable to a variety of clinical settings. The total telephone encounter time of the proposed intervention is approximately 30-45 minutes per encounter. In addition, the short duration of the intervention (24 weeks) also enhance ease of implementation in real-world practice. Most importantly, using clinic-employed CCMs will allow for easy incorporation of this strategy into practice, making it more sustainable over time, and immediately applicable.

- 4) **The intervention will leverage the therapeutic rapport between CCMs and HIV clinic patients to enhance the effectiveness of the proposed intervention.** CCMs typically have a nuanced knowledge of the HIV clinic patient's psychosocial barriers to care and how to resolve them. Of all the members of the HIV clinical care team, this depth of knowledge is usually exclusive to the CCM, given them the ability to quickly establish a unique therapeutic rapport with clinic patients. According to the New York State AIDS Institute, the goal of case management is "to promote and support independence and self-sufficiency". This goal aligns with the central tenets of the HINTS and CITIES interventions predicated on enhancing self-efficacy in accordance with the Health Belief Model (HBM), one of the preeminent psychological theories of health behavior. These parallel objectives make HIV CCMs ideal providers to implement the proposed interventions. The pre-existing therapeutic rapport between CCMs and their clinic patients is centered around the restoration of self-efficacy, a key component absent from both aforementioned studies. Given the work- time compression characteristic of the physician-patient interaction, CCMs may be more effective than providers in motivating lifestyle modification because they have more time to promote change in a systematic manner based on sound cognitive constructs. Although using CCMs will increase the amount of training needed to implement the intervention, the benefits of using these professionals to deliver chronic disease interventions have never been formally assessed. Examining the role of this therapeutic dynamic in the implementation of the behavioral intervention is novel and a primary focus of our study.

## **Study Objectives**

The overall objective of this study is to assess the impact of telephone-based case manager administered interventions in improving ASCVD risk factor outcomes among HIV-infected clinic patients.

### **2.1 Primary Objective**

To assess the effect of a telephone based CVD risk reduction intervention on decreasing systolic blood pressure (SBP) and fasting LDL-c levels from baseline.

### **2.2 Secondary Objective**

To assess the effect of a telephone based CVD risk reduction intervention on weight loss and change in 10-year ASCVD risk score.

## **Study Design**

### **3.1 General Design**

Fifty *high CVD* risk clinic patients will be randomized 1:1 to receive either a series of educational pamphlets on CVD risk reduction plus a telephone-based CVD risk reduction

curriculum delivered over 24 weeks [intervention arm], or the educational pamphlets alone [control arm]. Anthropomorphic data, blood pressure and lipid profiles will be obtained from patients at baseline and at the end of the study (24 weeks) to assess the efficacy of the intervention in reducing blood pressure and serum low-density lipoprotein levels (LDL).

### **3.2 Design Team Consultations**

We will conduct a series of participatory, iterative design consultation team meetings held over the course of 2-4 weeks. The design team will include a combination of 2-4 clinical social workers from Clinic 1K, 1-3 persons living with HIV. Each member of the design team will be recruited by personal invitation. The purpose of the design teams will be to provide refine the intervention designed by the study investigator and SW consultant. The design process will involve three main phases: brainstorming, conceptualization, and creation described below in study procedures. The results from the first two design team meetings will inform one additional design team meeting to iteratively refine the intervention. Informed consent will be obtained from all members of the consultation team. We anticipate that each design team session will take between 3-4 hours. Design team members will be compensated \$150 per session completed.

## **Subject Selection and Withdrawal**

### **4.1 Inclusion Criteria**

1. Age 40-75 years.
2. In care at the Duke Infectious Disease Clinic for at least 12 months.
3. HIV+ and on antiretroviral therapy for at least one year, with six consecutive months of documented viral suppression (HIV-1 RNA <200 copies/ml at time of enrollment).
4. Diagnosis of hypertension or hyperlipidemia.  
Hypertension is defined as: a) “Essential hypertension”, “Primary Hypertension” or “Hypertension” listed on their problem list in the electronic health record b) On antihypertensive medication for the indication of hypertension c) two consecutive ambulatory blood pressures of > 130/80 separated by 3 months or more.  
Hyperlipidemia is defined as: a) “Hyperlipidemia” or “Dyslipidemia” (with allowed modifiers) listed in patient’s problem list in EHR b) On any of the following lipid-lowering medications: statins, fibrates, PCSK-9 inhibitors, niacin, ezetimibe.
5. Able to speak and read English at least at the 6th grade level

### **4.2 Exclusion Criteria**

1. Prior diagnosis of acute coronary syndrome, stroke, peripheral vascular disease, and end stage renal disease, coronary revascularization (percutaneous coronary intervention or coronary artery bypass grafting) or congestive heart failure.
2. Pregnant, breastfeeding, or planning a pregnancy during study period.
3. Planning to move out of the area in the next 6 months.
4. No reliable access to telephone.
5. Terminal illness with life expectancy <4 months.
6. In a nursing home and/or receiving in-patient psychiatric care.
7. Severely hearing or speech impaired, or other disability that would limit participation in the intervention components.

8. Documented mental health diagnosis with component of psychosis.
9. Longitudinal follow up by a hyperlipidemia specialist (endocrinology or cardiology), hypertension specialist (nephrology or cardiology) or a cardiologist for any indication.

#### **4.3 Subject Recruitment and Screening**

**Pre-screening:** we will use the electronic medical records at our site to identify potential subjects for our study according to the inclusion/exclusion criteria. Potential subjects may also be recommended by providers within the Division of Infectious Diseases based on the inclusion/exclusion criteria. Potential subjects will initially be mailed a recruitment letter signed by his or her primary HIV provider. Potential subjects will have the opportunity to opt out of the study by calling a toll-free number.

In addition to receipt of letters, prospective participants will be approached with the permission of their providers during routinely scheduled clinical encounters, by a member of the study team. During such encounters, the study team will inform participants about the study and the reasons why they are eligible to participate. At that point, the patient will have the option to proceed with a baseline screening visit or not.

This study will also utilize cold-calling recruitment methods. This will include contacting the patients directly if they meet eligibility criteria to enroll them into this study. Research coordinator(s) will refer to patients' electronic medical records (EMR) to confirm that the patient(s) have not opted out from being contacted for research studies.

**Screening:** A research coordinator will contact all subjects who do not opt out. Following a telephone script, the research assistant will describe the study in detail, ensure the patient is eligible and willing to participate, and schedule a baseline study visit at the next clinical visit with an HIV provider where they will be enrolled following the informed consent process described below in section 5.1.

#### **4.4 Early Withdrawal of Subjects**

Throughout the course of the study, patients will be encouraged to complete the all study assessments. However, it is possible that a subject may discontinue study participation at any time for any reason. The reason for early withdrawal must be documented in the subject's case file, subject tracking document and subject withdrawal form on REDCap.

##### **4.4.1 Reasons for withdrawal:**

The voluntary nature of studies allows for participants to withdraw from the study at any point for any reason. Subjects may be withdrawn from the study if a serious adverse event (SAE) occurs. Subjects may be withdrawn if:

1. They withdraw their consent
2. In the opinion of the investigator, continuation of study participation would be hazardous to the participant, or compromise study findings.

The reason for any subject's discontinuation and the date of withdrawal will be recorded in the subject's case file. The subject's case file, which will be completed up to the point of withdrawal will be retained for six years. The study report will include reasons for subjects' withdrawals as

well as details relevant to the subjects' withdrawals. Any subject withdrawn from the trial prior to completion will undergo all procedures indicated in this protocol as being scheduled to occur at discharge or upon early withdrawal. Any subject withdrawn due to an adverse event (whether serious or non-serious) or any clinically significant abnormal laboratory test value will be evaluated by the principal investigator, and will be treated and followed up until the symptoms or values return to normal or acceptable levels, as judged by the Principal Investigator. Relevant post-study procedures will be performed, wherever possible, on subjects who elect to withdraw.

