#### **4.4.2 Handling of Withdrawals:**

If a subject is withdrawn from participation in the study at any time at his or her request, at the IRB or Principal Investigator's discretion, the reason(s) for discontinuation shall be documented thoroughly in the source documents and subject's case file. If a subject is discontinued because of an adverse event, this event will be followed until it is resolved or the subject is clinically stable and will also be documented in the source documents and the subject's case file.

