- h. This documentation and transmission to the study investigator should be conducted as soon as possible, but no later than 24 hours after completion of the phone call. Notification will be conducted ideally via institutional e-mail or MyChart messaging. The study investigator will be expected to give a response to such questions within 48 hours of receipt.
- i. The ISW will communicate all concerns about logistics of the study to the study coordinator in a timely manner
- j. The ISW will report all potential adverse events to the study team (study coordinator and study PI) as soon as they are aware as delineated in Section 7.2.

The following documents will be provided to the ISW by the study team prior to study launch:

- a. Telephone call intake forms
- b. Educational material associated with module administration
- c. Baseline assessment data for individual participants including participant's learning preferences
- d. Current contact information (phone and e-mail) of the study PI and the study coordinator
- e. A cell phone for the execution of study phone call with SMS transmission capability and associated data
- f. List of CVD-related community resources in Raleigh-Durham Metropolitan area
- g. Resource document with side effect profiles of major classes of medication used in cardiovascular disease primary prevention.
- h.

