### **6.3 Subject Population(s) for Analysis**

All randomized subjects with at least partial outcome data for the baseline and week 24 timepoints will be included in the analysis, regardless of missingness of the post-intervention timepoints.

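### Section 4.4.1 allows withdrawal from the study on an undefined non-safety ground or after any SAE without assuring week-24 outcomes, so removals before week 24 can bias the effect size

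*Combined protocol and SAP*

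**What the plan says.** Section 4.4.1 gives these grounds for withdrawal, apart from the participant's own withdrawal of consent:

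- "In the opinion of the investigator, continuation of study participation would be hazardous to the participant, or compromise study findings".
- "Subjects may be withdrawn from the study if a serious adverse event (SAE) occurs". The wording is permissive and does not require the event to be related to the study.

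Section 4.4.2 again refers to discretionary withdrawal: "at the IRB or Principal Investigator's discretion, the reason(s) for discontinuation shall be documented thoroughly".

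On what is collected afterwards, section 4.4.1 makes three statements:

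- The record: "The subject's case file, which will be completed up to the point of withdrawal will be retained for six years".
- Anyone withdrawn before completion "will undergo all procedures indicated in this protocol as being scheduled to occur at discharge or upon early withdrawal".
- "Relevant post-study procedures will be performed, wherever possible, on subjects who elect to withdraw".

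On who is analysed, section 6.3 says "All randomized subjects with at least partial outcome data for the baseline and week 24 timepoints will be included in the analysis", whether or not later visits are missing. Section 6.2 likewise drops observations that lack the week-24 timepoint. Section 6.1 states that the pilot's aim is to obtain an effect size for powering larger studies.

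**The concern.** The protocol does not separate stopping the telephone intervention from leaving follow-up. The only step it describes is withdrawal from the study. One permitted reason is the investigator's view that the findings would otherwise suffer, which is a judgement about the data and has no stated criteria. Nothing says that the person making it is unaware of allocation.

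The information behind such a judgement differs by arm. Intervention participants have 12 calls in 24 weeks (section 5.8), while controls receive printed or electronic material only (section 5.7). Under section 5.9 the social worker passes questions that cannot be answered to the investigator ("This documentation and transmission to the study investigator should be conducted as soon as possible, but no later than 24 hours" after the call) and reports potential adverse events on becoming aware of them. Controls have no such channel between baseline and week 24.

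If people are removed before week 24 for reasons tied to engagement or adverse events, more of them in one arm, and their week-24 values are not obtained, the remaining groups are no longer those that randomisation created. At stake is the effect size on which later trials would be planned.

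**Working it through.** **Plan's own figures (section 6.1).** 50 × (1 − 0.20) = 40 analysed. 7.6 / 15 = 0.507, given as 0.51. Both reproduce. Anticipated dropout from all causes is 0.20 × 25 = 5 per arm.

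**Is a week-24 value assured after withdrawal?**

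1. Early-withdrawal procedures are required, but the text available to this review does not list them. The visit flow chart of section 5.3 was not available.
2. The case file stops at withdrawal.
3. The sentence on post-study procedures, to be done as far as feasible, covers people who elect to leave. It does not name those removed by the investigator.
4. Section 5.8 gives follow-up visits a window of ±21 days, so the week-24 window opens at week 24 − 3 = 21. Nothing says that a withdrawal measurement before week 21 counts as week 24.

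So collection is possible but not assured. Without a week-24 value the person leaves the analysis under sections 6.2 and 6.3. Imputation under section 6.2 does not bring back someone whom these rules exclude.

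**Illustration A: removed participants have zero effect.** Assumptions, none from the documents: k of 25 intervention participants are removed, no controls are removed, and those retained have a 7.6 mmHg effect. SD is 15. The as-randomised effect is 7.6 × (25 − k)/25, and the reported effect is 7.6.

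| k | As randomised (mmHg) | d | Reported (mmHg) | d | Inflation (mmHg) |
|---|---|---|---|---|---|
| 3 | 7.6 × 22/25 = 6.69 | 0.45 | 7.6 | 0.51 | 0.91 |
| 5 | 7.6 × 20/25 = 6.08 | 0.41 | 7.6 | 0.51 | 1.52 |

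Section 6.1 gives 7.6 as the anticipated mean change. If it is read as the as-randomised effect, the reported value becomes 7.6 × 25/22 = 8.64 (d 0.58) or 7.6 × 25/20 = 9.50 (d 0.63). The ratio of reported to true effect is the same.

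Required sample size varies as 1/d². A later trial sized on the reported effect would have (22/25)² = 0.77 or (20/25)² = 0.64 of the participants it needs.

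**Illustration B: removal by engagement.** Simulated trials used 25 per arm, normally distributed SBP reductions and SD 15, with the k least engaged intervention participants removed. If engagement ranked people exactly by SBP response, the shift would be 1.23 mmHg for k = 1 and 5.04 for k = 5. With a weaker correlation r, the shift is r times that:

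- k = 1: 0.3 × 1.23 = 0.4 and 0.5 × 1.23 = 0.6 mmHg.
- k = 5: 0.3 × 5.04 = 1.5 and 0.5 × 5.04 = 2.5 mmHg.

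Over r = 0.3 to 0.5 and k = 1 to 5 the shift is therefore 0.4 to 2.5 mmHg, or 0.02 to 0.17 SD. The correlations and counts are assumptions.

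**Reference case.** Random removal of 5 per arm gave a mean estimate of 7.61 against a true 7.6, so no bias. The bias comes from selection; the loss of numbers alone does not cause it.

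**The case against.** The strongest reply is that the bias needs the clause to be used selectively, and nothing shows that it would be. Reasons for withdrawal must be recorded in the case file, the tracking document and REDCap (section 4.4) and appear in the study report (section 4.4.1), so an imbalance between arms would be visible. That stands as a safeguard on reporting, but it does not supply the missing outcomes.

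Four stronger readings are tempting and not supported:

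- *Withdrawal ends outcome collection.* No section says so. Section 4.4.1 requires some procedures at withdrawal, and the missing flow chart may specify them.
- *Poor responders could be removed.* No trial blood pressure or lipid measurement is scheduled between baseline and week 24, so no trial value identifies them in time. Once week 24 is measured, section 6.3 keeps the person in. Only removal linked to engagement or adverse events remains plausible.
- *The investigator hears within 24 hours about engagement and events, and from one arm only.* The 24-hour limit covers questions that the social worker cannot answer. Adverse events fall under a separate item. Staff also ask participants in both arms about adverse events at assessments, and blood pressure alerts apply at any study visit (section 7.2). The difference between arms is the extra channel that the calls provide.
- *The investigator is stated to be unmasked.* This is a fair inference from the role and from the absence of any masking provision, but it is not stated.

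The illustrations also rest on assumed counts, zero effect in those removed and one-sided removal. In both rows of Illustration A the as-randomised d stays above the plan's 0.3 threshold, so that comparison would not change.

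**Conclusion.** The point holds as a weakness in the withdrawal rule. It is not evidence that the estimate will be biased. An undefined non-safety ground and an SAE ground allow removal from the study, no masking is described, week-24 collection afterwards is not assured, and sections 6.2 and 6.3 then exclude the person. Together these allow exclusion that differs by arm.

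Size and direction cannot be derived from the documents. Under the stated assumptions, 3 to 5 removals in one arm overstate the effect by 0.9 to 1.5 mmHg, and engagement-linked removal of 1 to 5 shifts it by 0.02 to 0.17 SD. Removals after SAEs could move it either way. If the section 5.3 flow chart does require SBP and LDL-c for everyone withdrawn, and those values count as week 24, the gap narrows. The undefined ground would still need attention. The change is worth making because it is cheap and the effect size is the pilot's main product.

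**What to change.** In section 4.4.1:

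1. Delete the last limb of the investigator-opinion ground, the one about compromising the findings.
2. State that stopping the intervention, for whatever reason the investigator decides clinically, does not by itself end study visits. When or why the intervention stops remains a clinical decision and is not specified here.
3. State that blood pressure, weight and lipid panel at weeks 24, 48 and 72 continue unless the participant withdraws consent for them.

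In section 6.3, state that these data are analysed in the randomised arm.

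The cost is a one-paragraph amendment to section 4.4.1 and a sentence in 6.3. The visits are already planned (section 5.10) and paid at $25 each (section 10.3), so the three post-baseline visits come to 3 × $25 = $75 per person, already foreseen. The downside is that non-adherent participants stay in, so the observed effect may look smaller. The change does not deal with the week-24 exclusion of ordinary dropouts, which sections 6.2 and 6.3 would still apply.
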